Once CLCs are matched, the randomly selected CLC will be approached to solicit their participation with the strong endorsement of GEC leadership. We will approach the randomly selected experimental CLCs until up to 15 have agreed. If a CLC declines to participate, both members of the pair of matched CLCs will be dropped from consideration. The matched “control” case of those CLCs that agree to participate in the INTERACT program will not be approached. The “control” status of a CLC will be known to no one outside of the project research team and will not be divulged in any project description or publication.

Patient Selection: We do not anticipate excluding any Veterans in CLCs from the population to be included in the outcome analyses. The CLC is the unit of random assignment, meaning the intervention changes the skills of CLC staff. For each CLC agreeing to adopt the INTERACT program, it will be as if the CLC is introducing a focused quality improvement program to their staff. As such, no individual patient consent will be requested. We will separately examine hospitalization rates of Veterans classified as long stay or short stay based upon the pattern of recent admission and discharge data, but this will be regardless of their clinical condition or diagnoses.

Outcome Measures: The primary outcome (on which our statistical power estimates were based) will be the **overall hospitalization rate** calculated as the number of admissions to hospital from

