the CLC in a month per person year at risk of hospitalization in that month. This measure has been constructed per CLC using VHA-Medicare merged data from 2004 and afterwards obtained under [name] current HSR&D IIR. The measure will be constructed covering the period from at least the 24 months preceding the introduction of the INTERACT program until 24 months after the introduction of the INTERACT program. Since hospitalization rates vary substantially during flu season, we have fit an ARIMA model to reduce the heterogeneity of variance in this monthly measure of hospitalization, thereby reducing the heterogeneity of residual variance. An ARIMA model will be fit for each CLC in the study, then using the monthly difference between the observed to the expected value to compare between any two matched CLCs over time. The dependent measure is a facility aggregate which we will risk adjust using indirect standardization by stratifying the per CLC month measure separately for long stay and short stay person months at risk of hospitalization. [See the Statistical Considerations section below for a detailed presentation of the ARIMA model.]

[figure not shown]

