Aim #1: *To characterize VHA CLCs in terms of alternate measures of hospitalization for long stay and post-acute care residents, including Medicare hospitalizations, and to examine regional variations in these rates over the period 2007 thru 2012.* Using data from the merged VA SAS data system and Medicare claims, we will construct several different measures of hospitalization from CLCs that are applicable to both short and long stay residents. A facility level measure with limited risk adjustment will be calculated as the number of CLC patient days in the year divided by the number of unique admissions from CLC. This measure can be calculated per calendar year, per quarter or per month. Using 2007 and 2008 data, we’ve calculated this for all VHA CLCs, although some outliers suggest that there are likely inconsistencies in how unit transfers are coded which we will correct under the proposed study. Since hospitalizations vary by season, we’ll adjust for each CLC’s own seasonal variation (due to latitude) and characterize regional variation as well as variation attributable to the mix of short and long stay residents in the CLC and the proximity of the CLC to the VAMC. Of particular interest will be tracking changes over time in the rates of hospitalization since in the Medicare FFS system we have documented large increases over the last decade.[2] We will undertake the same analyses using the risk adjusted, per patient level hospitalization measures, estimating the proportion of short and long stay residents, respectively, that were hospitalized between 2007 and 2012 and to test whether the patient level, risk adjusted rate of hospitalization increased, given changes in the acuity of individual entering and residing in CLCs.

Aim #2A: *To modify, for VHA implementation, and pilot the on-line INTERACT quality improvement program intervention training materials.*

The INTERACT quality improvement program was initially developed under a grant from the Commonwealth Fund and has since been modified extensively through interventions implemented under the auspices of CMS-sponsored quality improvement programs and select state-based efforts designed to reduce hospitalizations from nursing homes.[3, 44] INTERACT’s web-based training

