
Examination of CLC Hospitalization Rates has been undertaken using the linked SAS and Medicare files for the year 2008. We accumulated all hospitalizations of Veterans directly from the CLC, both those occurring in VAMCs and those occurring in Medicare reimbursed hospitals. Given the relatively high use of Medicare hospital services in other VA populations, we were surprised to see that only 7% of all hospitalizations of Veterans in CLCs occurred outside of a VAMC. As expected, this varied from a high of nearly 50% in a small CLC to virtually no non-VAMC hospitalizations in many large CLCs. We calculated the number of acute events per Veteran and constructed the rate of hospitalization defined as the number of hospitalizations per person year. We did this by applying the Residential History File

algorithm initially developed using Medicare files and recently applied to VHA data by [name].[56] Across all CLCs, we found that there were .35 hospitalizations per Veteran but 23.5% of Veterans ever in the CLC in 2008 were hospitalized, suggesting that some individuals were hospitalized many times. Indeed, we find that the observed hospitalization rate is 1.3 per person year, ranging from a high of 1.1 to a low of .1! Both of these outliers had relatively few patient days suggesting that they house relatively few patients at any given time. In spite of these outliers, we should be able to effectively match CLCs with hospitalization rates in the mid-range.

Limitations:

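### The Aim 1 facility measure is written as days per admission, the reciprocal of a hospitalization rate: it runs in the wrong direction and is undefined in months or quarters with no admission

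*Combined protocol and SAP*

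**What the plan says.** Under Aim #1 the protocol promises a family of measures: "we will construct several different measures of hospitalization from CLCs that are applicable to both short and long stay residents". The facility-level one, with limited risk adjustment, is "calculated as the number of CLC patient days in the year divided by the number of unique admissions from CLC". On the time unit it says: "This measure can be calculated per calendar year, per quarter or per month". For 2007 and 2008 the team reports having already "calculated this for all VHA CLCs", with some outliers that it puts down to inconsistent coding of unit transfers. The same paragraph plans an adjustment for each CLC's own seasonal pattern and then states the purpose: "Of particular interest will be tracking changes over time in the rates of hospitalization".

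Elsewhere the facility rate has hospitalizations on top and time at risk underneath:

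- **Outcome Measures** (primary outcome): "calculated as the number of admissions to hospital from" and, across the page break, "the CLC in a month per person year at risk of hospitalization in that month".
- **CLC Selection, Matching and Random Assignment**: the second matching stage uses monthly re-hospitalization rates over days alive.
- **Preliminary Studies** (2008 data): "the rate of hospitalization defined as the number of hospitalizations per person year".

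The protocol does not say that Aim 1 deliberately uses a days-between-admissions measure, and it gives no rule for a period with no admissions.

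**The concern.** The Aim 1 formula is the reciprocal of what the rest of the protocol calls a hospitalization rate. Two things follow from the definition alone.

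1. **Direction.** More hospitalization gives a smaller value. Aim 1 is interested in whether CLC rates rose over 2007 to 2012, as the investigators report for Medicare fee-for-service. On this measure such a rise appears as a decline, and the CLCs with the most hospitalization rank lowest.
2. **Zero counts.** Admissions are the divisor, so a period without admissions has no value. Those are the periods with the least hospitalization, so the loss is selective. Monthly and quarterly use is expressly allowed, and a seasonal adjustment cannot be made from annual values alone.

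At stake is the reading of a descriptive aim, and agreement between the Aim 1 figures and the rate used in the trial itself.

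**Working it through.** The protocol gives no numerical value for the days-per-admission measure, so there is no figure to reproduce. The check covers direction and the frequency of undefined periods.

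**Inputs from the protocol**
- Rates: 1.3 per person-year overall, with a stated range of .1 to 1.1 (Preliminary Studies). The overall figure lies above its own stated maximum. That is a separate inconsistency, so results are shown at both 1.1 and 1.3.
- Reduction of 20%: the effect expected in the section on impact of findings, used only as an illustration.
- 50 beds: the minimum for the matching set. Aim 1 states no size limit.
- 2007 to 2012: 6 × 12 = 72 months.

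**Assumptions of this check**: full occupancy, Poisson admission counts, and an illustrative small CLC of 20 residents.

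**Step 1: direction (no distributional assumption).** Days per admission D = 365.25 / rate.
- At 1.3: D = 365.25 / 1.3 = 281.0. After a 20% fall the rate is 1.04 and D = 365.25 / 1.04 = 351.2.
- At 1.1: D = 332.0. After a 20% fall the rate is 0.88 and D = 415.1.
- In general D is multiplied by 1 / 0.8 = 1.25, so a 20% fall in the rate is always a 25% rise in the measure.

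**Step 2: undefined periods.** P(no admission) = exp(−residents × rate × length of period in years).

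| Residents | Rate per person-year | Month | Quarter | Year |
|---|---|---|---|---|
| 50 | 1.3 | 0.4% | about 0 | about 0 |
| 50 | 1.1 | 1.0% | about 0 | about 0 |
| 50 | 0.1 | 65.9% | 28.7% | 0.7% |
| 20 | 1.3 | 11.5% | 0.15% | about 0 |
| 20 | 1.1 | 16.0% | 0.4% | about 0 |
| 20 | 0.1 | 84.6% | 60.7% | 13.5% |

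For example, 50 residents at 1.3 give 50 × 1.3 / 12 = 5.417 expected admissions a month, and exp(−5.417) = 0.0044.

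Over 72 months, the chance that a 50-resident CLC has at least one undefined month is 1 − (1 − 0.0044)^72 = 27% at 1.3, and 52% at 1.1.

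**Step 3: the ratio turned over.** Admissions divided by person-years goes from 1.3 to 1.04 under the same fall, a change of −20%. A month with no admissions gives 0 and stays in the data.

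**The case against.** **It is probably a wording slip.** The Aim 1 paragraph itself speaks of rates, and the 2008 preliminary calculation was done with hospitalizations in the numerator. This is the likeliest explanation, and nothing shows that an analysis used the inverted ratio. But the protocol says the measure as described has already been computed for 2007 and 2008, so which formula was used needs confirming.

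**The reciprocal carries the same information.** On annual values, days per admission is a strictly decreasing function of the rate. It orders CLCs identically in reverse, and the trend can be read backwards. The definition is worded for a year; months and quarters are an option. This stands for annual values. It does not dispose of the sub-annual problem, because monthly values are allowed and seasonal adjustment is planned.

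**Reach is limited.** Aim 1 is descriptive and uses several measures. Its test of whether the risk-adjusted rate rose is made on patient-level data and does not use this ratio. This stands in full.

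**Stronger readings that the documents do not support.**
- A reader might infer that the Aim 1 answers on trend and variation would simply be wrong. For annual values only the direction and ordering are reversed.
- A reader might infer that differences between CLCs would be heavily distorted, since averaging monthly ratios over the months that have a value is biased. At 1.3 with 50 residents, a simulation gives a mean of 357 days against a true 281. But Aim 1 specifies no such averaging, and pooling days and admissions over the year avoids it. A contrast between .1 and 1.3 would also pair an outlier, described as having few patient days, with a rate above the protocol's own stated maximum.
- A reader might infer that the inverted ratio caused the outliers in the 2007 and 2008 values. A small divisor can produce extreme values, but the protocol attributes them to coding and offers nothing to test either explanation.

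**Conclusion.** The formula is wrong as written, and the severity is minor. The reversal of direction follows from the definition and needs no assumption. The loss of zero-admission periods also follows from the definition, but its size rests on Poisson counts, full occupancy and the chosen CLC size. At the protocol's central rates it is a fraction of a percent to about one percent of months in a 50-resident CLC, and roughly one month in six to nine in a 20-resident CLC. It becomes large only at very low rates. For annual values it is negligible, except in a CLC that is both very small and at the bottom of the range.

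The primary outcome, the matching variable, the Aim 4 comparison and the power simulation do not use this ratio. The trial's main result is not in question.

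**What to change.** - Replace the Aim 1 definition with hospital admissions from the CLC divided by patient days at risk in the same period, scaled to person-years, as in Outcome Measures. Periods with no admissions then take the value 0 and are kept.
- Confirm which formula produced the 2007 and 2008 values. If it was days per admission, recompute them and look again at the reported outliers.

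This costs one corrected sentence and one check of existing output, with no new data. A count model with log patient-days as an offset would be a reasonable way to analyse monthly or quarterly data, but it is optional and the correction does not depend on it.

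### Aim 1 describes variation between CLCs with a ratio that is undefined when there are no admissions, and no step separates small-count noise from true differences

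*Combined protocol and SAP*

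**What the plan says.** The Aim #1 section of the combined protocol and SAP defines "A facility level measure with limited risk adjustment" as "the number of CLC patient days in the year divided by the number of unique admissions from CLC". It adds: "This measure can be calculated per calendar year, per quarter or per month". The measure has already been computed for all VHA CLCs from 2007 and 2008 data, and the section comments that "some outliers suggest that there are likely inconsistencies in how unit transfers are coded which we will correct under the proposed study".

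The plan then adjusts for each CLC's own season and will "characterize regional variation as well as variation attributable to the mix of short and long stay residents in the CLC", together with proximity to the VAMC. Change over time is named as of particular interest. A second strand follows: "We will undertake the same analyses using the risk adjusted, per patient level hospitalization measures".

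Preliminary Studies reports hospitalizations per person-year for 2008 and says of the highest and lowest CLC: "Both of these outliers had relatively few patient days suggesting that they house relatively few patients at any given time".

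For Aim 1 the document states no precision weighting, intervals, random effects, shrinkage or minimum CLC size. The limit of at least 50 beds belongs to the matching (CLC Selection, Matching and Random Assignment). The ARIMA models (Outcome Measures, Aim #4) and the facility-clustered standard errors (Aim #4) belong to the outcome analysis.

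**The concern.** The spread of observed CLC values is true variation plus sampling noise, and the noise is largest where patient days are fewest. Aim 1 lists season, region, stay mix and proximity as sources of variation, but not sampling error. A description built on the observed values therefore cannot show how much of the spread between CLCs is real.

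Two further points follow from the text. With admissions in the denominator, the ratio has no value in a period without an admission, which is a practical problem for small CLCs by month. And the coding correction is announced without a criterion or a statement of which CLCs it covers. If an outlying value were the trigger, chance extremes would be edited, while the same miscoding at CLCs with ordinary values would stay.

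At stake is the descriptive result of Aim 1: the size of between-CLC variation and which CLCs look extreme.

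**Working it through.** **The document's own figures.** Preliminary Studies gives an overall 2008 rate of 1.3 per person-year with CLC rates from 0.1 to 1.1. An overall rate cannot lie above the highest CLC rate, so these figures cannot be reproduced together, and the text does not show which is wrong. The illustration therefore uses assumed rates. The same section gives .35 hospitalizations per Veteran and 23.5% ever hospitalized: .35/.235 = 1.49 stays per hospitalized Veteran. Repeat stays of this kind make counts more variable than Poisson.

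**Inputs.** From the document: the time units (year, quarter, month) and the Aim 1 span, 2007 through 2012, or six years. Assumed: 1.0 or 0.5 hospitalizations per person-year, census 20 or 50, true between-CLC CV 25%, Poisson counts. The calculation is for admissions per person-year, the inverse of the Aim 1 ratio, because the ratio itself has no finite variance once zero counts are possible.

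**Formulas.** Expected count m = rate × census × years. Noise CV² = 1/m. Observed SD / true SD = √(0.25² + 1/m) / 0.25.

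| Rate, census | Year | Quarter | Month | Six years pooled |
|---|---|---|---|---|
| 1.0, 20 | m = 20: 1.34 | m = 5: 2.05 | m = 1.67: 3.26 | m = 120: 1.06 |
| 1.0, 50 | m = 50: 1.15 | m = 12.5: 1.51 | m = 4.17: 2.20 | m = 300: 1.03 |
| 0.5, 20 | m = 10: 1.61 | m = 2.5: 2.72 | m = 0.83: 4.49 | m = 60: 1.13 |

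For example, for the first row by month: √(0.0625 + 0.6)/0.25 = 0.814/0.25 = 3.26; pooled: √(0.0625 + 0.00833)/0.25 = 0.266/0.25 = 1.06. Pooling assumes that each CLC's true rate is stable over the six years.

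**Range over the true spread.** Reliability (the share of observed variance that is true) = τ²/(τ² + rate/person-years). At an assumed rate of 0.6 and a between-CLC SD τ of 0.1 to 0.2, it is 0.25 to 0.57 by year and 0.03 to 0.10 by month at census 20. At census 50 it is 0.45 to 0.77 and 0.06 to 0.22.

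**Undefined ratios.** P(no admission in a month) = exp(−m). At rate 1.0: census 20, exp(−1.67) = 19%; census 50, exp(−4.17) = about 2%. At rate 0.5 and census 20, exp(−0.83) = 43%.

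**Could chance alone produce the printed range?** Simulation gave every one of 64 CLCs the same true rate of 0.6, with log-uniform sizes (number, rate and sizes all assumed). With 5 to 200 person-years per CLC, the average minimum and maximum were 0.16 and 1.16, and both extremes fell in the smaller half of CLCs in 97% of runs. With at least 50 person-years everywhere, they were 0.41 and 0.81. The answer depends on CLC sizes that the document does not give.

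**The case against.** The strongest case on the other side is this. Aim 1 is descriptive. Its measure already carries limited risk adjustment and each CLC's own seasonal adjustment, and a risk-adjusted patient-level strand runs beside it. The large multipliers need single months at a census of 20, a size that appears nowhere in the document. Over the whole period the inflation nearly vanishes. The coding remark concerns how unit transfers are recorded. The plan already uses the Bed Section files to tell acute stays from inpatient rehabilitation (VHA Utilization and Costs), and the Residential History File has been applied to the combined VA-Medicare data.

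Much of this stands. A reader might infer four stronger things that the text does not support:

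- That Aim 1 and Preliminary Studies contradict each other about the outliers. One concerns days per admission in 2007 and 2008, the other hospitalizations per person-year in 2008. The CLCs are not shown to be the same, and a CLC can be both small and miscoded.
- That every outlier is to be treated as an error, or that only outlying CLCs will be corrected. The text speaks of some outliers and likely inconsistencies, and is silent on which CLCs the correction covers.
- That the values are raw or deliberately unweighted. Some adjustment is stated; weighting is not mentioned.
- That regional variation is inflated to the same degree. Noise averages over the CLCs in a region, and no calculation here supports a regional figure.

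What does not stand is that the existing adjustments deal with the problem: seasonal and case-mix adjustment do not remove small-count noise. Nor is pooling a full answer, since Aim 1 also wants to follow change over time.

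**Conclusion.** The point holds as a modest improvement to a descriptive aim. The chosen ratio has no value in CLC-periods without admissions, and nothing planned for Aim 1 separates small-count noise from true variation between CLCs. Under the assumptions shown, the effect is small by year at census 50 (1.15 times the true SD), moderate by year at census 20 (1.34), and large by month (2.2 to 3.3 at 1.0 per person-year). Overdispersion from repeat stays would raise these figures; a larger true spread or census would lower them.

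Chance may contribute to the extreme 2008 rates, since both came from CLCs with few patient days, but its share cannot be determined without CLC sizes. It would go too far to conclude that Aim 1 cannot estimate variation, or that the trial's main result is at risk. Matching used CLCs of at least 50 beds, clustered on patient days, with five years of rates, and the primary test is a paired difference in difference. Neither is shown to be affected.

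**What to change.** Replace the ratio by a count model: admissions per CLC-period, log patient-days as offset, negative binomial (or Poisson if overdispersion proves negligible), random effects for CLC and region, and season, stay mix and proximity as covariates. Periods with no admissions then enter as ordinary zeros, and the measure points the same way as the primary outcome, admissions per person-year. Report the variance components, and shrunken CLC rates with intervals beside the observed rates.

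State the unit-transfer correction as a coding criterion based on the Bed Section files, and apply it to every CLC and year whatever its rate.

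The cost is analysis wording and a standard model on data already being assembled. The one small drawback is that shrunken rates are slightly harder to explain, which showing the observed rates alongside largely meets. Intervals alone, pooled years or a minimum CLC size would be simpler partial remedies, but they do not estimate the between-CLC variance.
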